6.2 Final Analysis

The final analysis will include all described analyses of this IAP except for the model of the TSQM v1.4 at Month 6 Visit (Section 0), which will only be done for the interim analysis. The TSQM v1.4 at Month 6 Visit will be included in a repeated model at the final analysis (Section 14.3.2).

The final analysis will be based on all data available in the database at the time of the final database lock.

7

Changes to the Planned Analyses in the Clinical Trial Protocol

Handling of data of subjects with a delayed 2nd treatment course:

The study protocol provides the following guidance how data of subjects with a delayed 2nd treatment course beyond 3 months should be handled in the statistical analyses.

Section 5.5.1: "Subjects with lymphopenia lower than the above-mentioned limit and/or occurrence of the above-mentioned infections, resulting in delay of scheduled second year treatment course beyond 3 months will be excluded from, tertiary or exploratory endpoint analysis."

Section 8.5.1: "Subjects for whom treatment is delayed by over 3 months may not have all assessment data captured and as such, these observations will be treated as missing."

As the data of the 1st treatment course are expected to provide valid efficacy information and the treatment delay of the 2nd year does not affect the 1st year course, it is decided that all data from the 1st treatment course should be included in all efficacy analyses while data from the 2nd treatment course will be excluded from all efficacy analyses for subjects with a delayed 2nd treatment course beyond three months.

For safety analyses, all data from both Treatment Courses will be used independently from the delayed start of Treatment Course 2. Section 9 defines the details of the data handling of subjects with a Delayed Treatment Course 2.

1-year interim analysis:

A 1-year IA was added during the course of the study without a corresponding protocol amendment.

COVID-19 pandemic:

Additional analyses to describe the potential impact of the COVID-19 pandemic added.

8 Protocol Deviations and Analysis Sets

8.1 Definition of Protocol Deviations

Major protocol deviations are protocol deviations (PD) that might significantly affect the completeness, accuracy, and/or reliability of the study data or that might significantly affect a subject's rights, safety, or well-being.

Major protocol deviations and any action to be taken regarding the exclusion of subjects or affected data from specific analyses are defined in the project-specific Protocol Deviation Specification.

All protocol deviations are documented in Study Data Tabulation Model (SDTM) datasets whether identified through site monitoring, medical review or programming. Tables and listings of PDs are defined in Section 10.2.

8.2 Definition of Analysis Sets and Subgroups

Enrolled Set (ES)

All subjects enrolled in the study, i.e. all subjects with a signed informed consent.

Intent-to-treat Set (ITT)

All subjects classified as eligible (i.e. medication assigned by iRT at the Baseline Visit).

Full Analysis Set (FAS)

All subjects from the ITT treated with at least one dose of study medication.

Treatment Completer Set – Year 1 (TCS-1)

All subjects from the FAS who completed the full Treatment Course of the first year (Treatment Course 1). Subjects will be classified as Treatment Completer for the first year, if they have a compliance greater than or equal to 100% for Treatment Course 1.

Treatment Completer Set – Year 2 (TCS-2)

All subjects from the FAS who completed the full Treatment Course of the first and the second year. Subjects will be classified as Treatment Completer for the second year, if they have a compliance greater than or equal to 100% for Treatment Course 1 and Treatment Course 2 and received the treatment without delay (see Section 9 for definition).

Safety Analysis Set (SAF)

All subjects treated with at least one dose of study medication.

Unless otherwise specified, all efficacy analyses will be performed on the FAS. The primary analysis will be repeated on the Treatment Completer Sets and on the ITT, if different, to evaluate

the sensitivity of the primary results to deviations of the planned treatment regimen. Further details are given in the respective sections. All safety analyses will be performed on the SAF.

Additional Subgroup Analysis Sets

Subgroup analyses will be performed on subgroups as defined below.

Previous treatment with Disease Modifying Drugs (DMDs):

- **DMD pre-treated:** Subjects will be categorized as DMD pre-treated if they have taken DMDs any time before start of study medication. Details of the definition of DMDs are specified in Appendix 1 (Section 18.1).
- **Pre-treatment naïve:** all subjects not classified as DMD pre-treated.

Unless otherwise indicated, all descriptive statistical analyses will be presented separately for pre-treatment naïve and DMD pre-treated subjects.

Month 12 MSQoL assessment after start of COVID-19 pandemic:

- **Yes:** Date of Month 12 MSQoL assessment (if missing, Month 12a Visit End Date) after start of COVID-19 pandemic (see Section 9 for definition).
- **No:** Otherwise.

This subgroup is used in 1-year IA and any ePRO analyses dedicated to 1-year data as specified in the respective sections.

Specific analyses as specified in the respective sections will be repeated for these subgroups.

9 General Specifications for Data Analyses

Treatment groups

The treatment group will be labeled as Mavenclad®.

Significance level

All statistical tests mentioned in this IAP are to be regarded as exploratory. All statistical tests will be performed 2-sided. If confidence intervals are to be calculated, these will be 2-sided with a confidence probability of 95%, unless otherwise specified in this IAP.

Presentation of continuous and qualitative variables

Continuous variables will be summarized using descriptive statistics, i.e. number of subjects, number of subjects with missing and non-missing values, mean, standard deviation, median, 25th Percentile - 75th Percentile (Q1-Q3), minimum, and maximum.

Qualitative variables will be summarized by counts and percentages.

Unless otherwise stated, the calculation of proportions will be based on the number of subjects of the analysis set of interest. Therefore, counts of missing observations will be included in the denominator and presented as a separate category.

In case the analysis refers only to certain Visits percentages will be based on the number of subjects still present in the study at that Visit, unless otherwise specified.

Definition of Baseline

The last non-missing measurement prior to start of study medication will serve as the Baseline measurement. Measurements performed on the day of first intake of study medication are assumed to be “prior to start of study medication” as long as it has not been confirmed that the procedure was performed afterwards. This assumption is justified as following the sequence of procedures as specified in the study protocol. The intake of study medication should be the last procedure on the visit day.

Definition of change from Baseline

Change from Baseline = Visit value – Baseline value

Percent Change from Baseline = $100 * (Visit value - Baseline value) / Baseline value$

Definition of visit dates

The visit start date is the date of the first assessment which belongs to the corresponding visit.

The visit end date is the date of the last assessment which belongs to the corresponding visit.

Definition of duration

Duration will be calculated by the difference of start and stop date + 1 in days (if not otherwise specified).

Treatment Period

The treatment period begins with the start of study medication on Study Day 1 and continues through to the completion of the treatment period at the Month 24 Visit (see protocol Section 7.1.3). Start of study medication is the date of first intake of study medication. Start of study medication in Year 2 is the date of first intake of study medication at or after the Month 12 Visit.

Treatment Period:

- Start = Start of study medication,
- End = Visit end date of Month 24 Visit or Early Termination (ET) Visit in case of early discontinuation, or the study discontinuation date, if the ET Visit was not performed.

Course 1 Treatment Period:

- Start = Start of study medication,
- End = Start of study medication at or after the Month 12 Visit -1 day or if the subject did not receive Treatment Course 2: Start of study medication of Treatment Course 1 + 457 days (which is obtained by 360 (12 months) + 90 (3 months) + 7 (visit window)), or date of the study discontinuation, if earlier.

Course 2 Treatment Period:

- Start = Start of study medication at or after the Month 12 Visit,
- End = End of Treatment Period.

Definition of Delayed Treatment Course 2

- The Treatment Course 2 will be defined as delayed, if the start of study medication is delayed by more than 3 months (=90 days) or did not start at all i.e.:
 - Start of Study Medication of Treatment Course 2 > Start of Study Medication of Treatment Course 1 + 457 days (which is obtained by 360 (12 months) + 90 (3 months) + 7 (visit window)), or
 - Treatment Course 2 never started (i.e. no study medication taken at or after the Month 12 Visit).

Data handling in case of a Delayed Treatment Course 2

For subjects with a Delayed Treatment Course 2, only data observed during the Course 1 Treatment Period will be analyzed in all efficacy analyses. Efficacy data after the Course 1 Treatment Period will be counted as missing in the statistical analyses and marked in the listings. In all efficacy analyses defined by Period, the subjects will be classified as if they discontinued at the end of the Course 1 Treatment Period. For subjects without a delay the whole Treatment Period will be analyzed.

For all other analyses (except efficacy) the data is not limited to the Course 1 Treatment Period for subjects with a Delayed Treatment Course 2.

Definition of start of COVID-19 pandemic

The start of COVID-19 pandemic will be defined by country as the earliest date of either the date of the first death from COVID-19 occurred in each country according to the published data by European Centre for Disease Prevention and Control on 26th June 2020 (<https://www.ecdc.europa.eu/en/publications-data/download-todays-data-geographic-distribution-covid-19-cases-worldwide>) or 11th March 2020 (when the WHO declared COVID-19 pandemic).

Visit timing with respect to COVID-19 pandemic

A visit is defined to be performed after the start of COVID-19 pandemic if the visit end date is greater than the start of COVID-19 pandemic date.

Conversion factors

The following conversion factors will be used to convert days into months or years for all observations except Visit related dates:

- 1 month = 30.4375 days,
- 1 year = 365.25 days.

Time window

- Day 1 is the day of start of study medication, the day before is Day -1 (no Day 0 is defined).
- Study day / Treatment day is defined relative to Day 1.

The visit schedule is defined as follows:

- 1 month = 30 days,
- 1 year = 360 days,

relative to the start date of the Baseline Visit for Treatment Course 1 and relative to the start date of the Month 12b Visit as defined in the eCRF (see also Section 15.3) for Treatment Course 2.

In each analysis, should assessment be delayed, subjects' assessment data will be treated as though it occurred at the time point specified (i.e. out of visit windows will be not excluded or adjusted for any analyses) and inferences will be conducted accordingly. Thus, further time windows will not be specified.

All observations from unscheduled Visits will be included only in the analyses of Visit independent summaries (e.g. counts of events, progressions or worst value during Treatment Period) unless for the last assessment available. In this case the missing ET visit will be imputed by the unscheduled visit.

If not specified otherwise, the assessments of the ET visit will be mapped to the nearest next planned post-baseline visit with a missing assessment before or after the ET visit of the individual assessment for all statistical analyses and descriptive summaries. As not all assessments of the ET

are performed at each visit, the different assessments of the ET can be assigned to different visits. If the duration (in days) between the ET visits and two missing planned visits are equal, then the assessment will be assigned to the later visit.

Handling of missing data

Unless otherwise specified in respective sections, missing data will not be replaced.

The handling of missing covariate and stratification factor information is described below.

The handling of missing DMD end date is described in Section 12.

Incomplete or missing onset dates of relapses from “MS Relapse Report” will be imputed as follows:

- In cases where the onset date is completely or partially missing but the onset month and year, or the onset year are equal to the start of study medication then the onset date will be replaced by the start date of study medication.
- In all other cases the missing onset day or missing onset month will be replaced by 1.

In all subject data listings, imputed values will be presented. In all listings imputed information will be flagged.

Missing statistics, e.g. when they cannot be calculated, should be presented as “nd”. For example, if n=1, the measure of variability (e.g. SD) cannot be computed and should be presented as “nd”.

Where tables are presented over time, the total of missing and non-missing observations at each time-point should reflect the population still in the study at that time. This does not apply when imputations are made beyond study withdrawal.

Data Handling in case of major PDs

Electronic Patient Reported Outcomes (ePRO) assessments performed completely in non-native language will not be used for the statistical summaries or analyses as planned in this IAP and will be flagged accordingly in any listings.

Any other PD will not be considered in the planned statistical analyses.

Covariates and stratification factors

- Age

Age (years) at time of Informed Consent (loaded from iRT). Missing age will be replaced as follows if used as a covariate:

1. Age will be estimated from the year of birth (year of IC – year of birth), as recorded in the electronic Case Report Form (eCRF)
2. If year of birth is missing, age will be imputed by the mean age of the FAS.

- **Pooled centers**

Some centers will have few eligible subjects only. Therefore, the centers will be pooled together in geographical groups by country and the Scandinavian countries will be further pooled together to one Scandinavian pool.

Software(s)

All analyses will be performed using SAS® Software version 9.3 or higher.

10 Trial Participants

The subsections in this section include specifications for reporting subject disposition and treatment/study discontinuations. Additionally, procedures for reporting protocol deviations are provided.

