5.5.2 Withdrawal from the Trial

Subjects may withdraw from the trial at any time without giving a reason. Withdrawal of consent will be considered withdrawal from the trial. The Investigator should make every attempt to clarify the level of withdrawal: e.g., whether or not data collected can be evaluated, banked samples can still be retained and evaluated, if the subject can still be contacted by phone for checking his/her status (e.g., alive or not), or to return for scheduled visits. In case of withdrawal from the trial for reasons other than consent withdrawal, the assessments scheduled for the Early Termination visit should be performed immediately. In any case, the appropriate eCRF section must be completed. Subject will be asked to confirm that any samples collected but not yet analyzed can be utilized.

Subjects withdrawn from trial medication will continue the scheduled assessments until his/her planned trial completion. These subjects will be managed based on the Investigator's clinical judgment and per local guidelines, and any new medication prescribed in such a period will be recorded. In any case, the appropriate eCRF section must be completed.

The Investigator may withdraw a subject at any time if this is considered to be in the subject's best interest.

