8.4 Analysis Sets

Enrolled Set: All subjects enrolled.

Intent-to-treat Set (ITT): All subjects classified as eligible.

Full Analysis Set (FAS): All subjects from the ITT treated with at least one dose of trial treatment.

Treatment Completer Set – Year 1: All subjects from the FAS who completed the full treatment course of the first year.

Treatment Completer Set – Year 2: All subjects from the FAS who completed the full treatment course of the first and the second year.

Safety Set: All subjects treated with at least one dose of trial treatment.

The primary analyses and all efficacy analyses will be performed on the FAS. The primary and secondary analyses will be repeated for the Treatment Completer Sets and the primary for the ITT, if different. All safety analyses will be performed on the Safety Set.

Subjects who have withdrawn consent for the trial will be included in the analysis unless it was specified by them that their data not be used, after clarification of the level of withdrawal by the Investigator.

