- Duration (days)= (date of last tablet in period – date of first tablet in period + 1)

Counts of tablets and compliance will be calculated first for each treatment week:

- Compliance (%) = $100 * \text{number of tablets taken during the treatment week} / \text{number of planned tablets for the treatment week}$

If a subject discontinued the treatment before the start of the respective treatment week, compliance will not be derived for this week. If the subject did not take any tablet during the respective treatment week, but had not discontinued the treatment before, compliance will be 0. If the subject was treated during the respective treatment week, but the number of tablets is unknown, compliance will be missing.

Compliance for each year (course) and total will be calculated for all subjects that started the respective treatment period (i.e. taken at least one tablet) as an average of available records obtained for the corresponding treatment weeks. That means, treatment weeks after the subject's treatment discontinuation are not included in the derivation, records of 0 compliance for the corresponding treatment weeks are included in the derivation as such, and missing records result in missing compliance for the respective treatment period.

In addition, compliance will be categorized as follows:

- < 60%
- [60%-80%[
- [80%-90%[
- [90%-110%]
- > 110%
- Missing

The number of planned tablets is based on the weight at the beginning of each treatment course (Table 3).

Table 3: Dose of Mavenclad® per treatment week by subject weight in each treatment year

Weight range kg	Dose in mg (number tablets) per treatment week	
	Treatment week 1	Treatment week 5
40 to <50	40 mg (4 tablets)	40 mg (4 tablets)
50 to <60	50 mg (5 tablets)	50 mg (5 tablets)
60 to <70	60 mg (6 tablets)	60 mg (6 tablets)
70 to <80	70 mg (7 tablets)	70 mg (7 tablets)
80 to <90	80 mg (8 tablets)	70 mg (7 tablets)
90 to <100	90 mg (9 tablets)	80 mg (8 tablets)
100 to <110	100 mg (10 tablets)	90 mg (9 tablets)
110 and above	100 mg (10 tablets)	100 mg (10 tablets)

The number of subjects with the same planned dosing schema in both Treatments Courses and a different planned dosing schema (i.e. subjects exchanged weight range as defined in the table above) in Treatment Course 2 will be presented for all subjects, who have started Treatment Course 2 (i.e. taken at least one tablet in Treatment Course 2).

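### The completer sets admit subjects who stop treatment between the two weeks of a course, because course compliance ignores weeks after discontinuation

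*SAP*

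**What the plan says.** Protocol 8.4 defines the Year 1 completer set as "All subjects from the FAS who completed the full treatment course of the first year"; the Year 2 set requires both years' courses. SAP 8.2 keeps that description and then adds the classification rule. A subject enters TCS-1 "if they have a compliance greater than or equal to 100% for Treatment Course 1", and enters TCS-2 with "compliance greater than or equal to 100% for Treatment Course 1 and Treatment Course 2 and received the treatment without delay". The primary analysis is to be repeated on these sets to evaluate "the sensitivity of the primary results to deviations of the planned treatment regimen".

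Compliance is defined in SAP 13. Each course has two treatment weeks, week 1 and week 5. Weekly compliance is tablets taken over tablets planned, and course compliance is the average of the weekly records available. On discontinuation the SAP says: "If a subject discontinued the treatment before the start of the respective treatment week, compliance will not be derived for this week". It repeats this for the course average: "treatment weeks after the subject's treatment discontinuation are not included in the derivation". A week without tablets scores 0 only if the subject had not already discontinued.

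**The concern.** The description and the classification rule disagree for a subject who stops treatment between the two weeks of a course. By description this subject did not complete the course. By the rule, the only available record is week 1 at 100%, so course compliance is 100% and the subject is a completer. No other visible text settles the conflict.

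Stopping mid-course is a plain departure from the planned regimen. Sets meant to show whether the primary result survives such departures should not retain it, particularly when the same rule removes a subject who missed one tablet. Membership also turns on the recorded discontinuation date and not on the drug taken: two subjects with identical week-1-only intake are classified differently according to whether a discontinuation is dated before week 5.

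**Working it through.** **Inputs.** Planned tablets per week come from the dosing table in SAP 13 (Table 3), which matches Protocol Table 1. The compliance formulas are in SAP 13, the membership cut-off of 100% in SAP 8.2, and the delay rule in SAP 9. The plan gives no figure of its own to reproduce here.

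**Formulas.** Let w1 and w5 be the planned tablets in the two weeks of a course.

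- Stop after week 1, SAP 13 compliance: only week 1 is available, so 100 × w1/w1 = 100%.
- Share of course tablets actually taken: w1/(w1 + w5).
- Same intake, but no discontinuation recorded before week 5: (100 + 0)/2 = 50%.
- One week-5 tablet missed: [100 + 100 × (w5 − 1)/w5]/2.

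| Weight (kg) | w1, w5 | Stop after week 1: compliance | Stop after week 1: share of course | One week-5 tablet missed: compliance |
|---|---|---|---|---|
| 40 to <50 | 4, 4 | 100% | 50.0% | 87.5% |
| 50 to <60 | 5, 5 | 100% | 50.0% | 90.0% |
| 60 to <70 | 6, 6 | 100% | 50.0% | 91.7% |
| 70 to <80 | 7, 7 | 100% | 50.0% | 92.9% |
| 80 to <90 | 8, 7 | 100% | 53.3% | 92.9% |
| 90 to <100 | 9, 8 | 100% | 52.9% | 93.8% |
| 100 to <110 | 10, 9 | 100% | 52.6% | 94.4% |
| 110 and above | 10, 10 | 100% | 50.0% | 95.0% |

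In every weight band the mid-course stopper is in TCS-1, and the subject who missed one tablet is out.

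**TCS-2.** The delay condition in SAP 9 asks only whether Course 2 started, and when. A Course 1 stopper who never starts Course 2 counts as delayed and is removed. A subject who completes Course 1, starts Course 2 on time, takes week 1 and stops is not removed: compliance is 100% for both courses. The share of two-year tablets taken is (Course 1 total + week 1 of Course 2)/(both course totals):

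- same band both years: from 21/28 = 75.0% to 23/30 = 76.7%;
- one-band shift: from (8 + 5)/(8 + 10) = 13/18 = 72.2% to (17 + 8)/(17 + 15) = 25/32 = 78.1%.

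**Route to the estimate.** For a Course 1 stopper, SAP 9 ends the Course 1 period at start + 457 days (360 + 90 + 7), or at study discontinuation if earlier. It states: "Efficacy data after the Course 1 Treatment Period will be counted as missing in the statistical analyses". Such a subject can affect the TCS-1 Month 24 estimate only indirectly, through Month 12 data in the repeated-measures model. For a Course 2 stopper there is no such cut, and Protocol 5.5.2 says: "Subjects withdrawn from trial medication will continue the scheduled assessments until his/her planned trial completion". If that subject stays in the trial, Month 24 MSQoL-54 data enter the TCS-2 analysis directly.

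**Possible shift in the TCS-2 mean (assumed inputs, not from the documents).** Suppose 0.5–5% of TCS-2 are such stoppers and their mean change differs from that of true completers by 5–10 points. The shift is fraction × difference: 0.005 × 5 = 0.025 points up to 0.05 × 10 = 0.5 points, on a 0–100 scale.

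**The case against.** Four points can be made for the plan.

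- **The descriptive sentence could act as a condition of its own.** A programmer who applied it together with the compliance cut-off would exclude the mid-course stopper. This is possible, but the second sentence is the only one that states how subjects are classified, and SAP 13 contains the only visible definition of compliance. At best the two sentences conflict and need reconciling.
- **Text is redacted.** SAP 8.2 defers details to later sections, and part of what follows the primary analysis in Section 14 is blacked out. The set definitions and the compliance derivation are themselves visible, however, and neither requires both weeks.
- **The trigger is narrow.** The next scheduled visits after each course starts are Month 2 and Month 14, so no scheduled visit falls between the two treatment weeks. If discontinuation is dated at the visit where it is recorded, week 5 scores 0 and the subject is already out. If it is dated at the last dose, the problem arises. The documents do not say which, so this limits how often the problem occurs but does not remove it.
- **Month 24 questionnaires after stopping are not certain.** Protocol 5.2 speaks only of safety assessments and mandatory monitoring for subjects who discontinue the drug. Protocol 5.5.1 and 5.5.2 are broader and keep them in the scheduled assessments.

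It is also true that the trial is exploratory, that the completer analyses are supportive, and that tablet counts, cumulative dose and the compliance listing would make such cases detectable. Detection does not correct set membership.

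**Conclusion.** The concern holds. Followed as written, the rule places a subject with 50.0–53.3% of Course 1 in TCS-1, and a subject with 75.0–76.7% of the two-year tablets (72.2–78.1% with a one-band weight change) in TCS-2. It excludes subjects who missed a single week-5 tablet. This rests on a discontinuation dated before week 5 and on the absence of a reconciling rule in the redacted text.

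The consequence is limited. The primary analysis on the Full Analysis Set does not change, the number of affected subjects is unknown, and under the assumed ranges the TCS-2 mean moves by about 0.03–0.5 points. It should still be corrected, because the error lies in the very feature these sets exist to test.

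**What to change.** Add one sentence to SAP 8.2: for TCS membership only, a planned treatment week not taken because of discontinuation counts as 0%, and both planned weeks of the course must be complete, each with at least 100% of its planned tablets (both courses for TCS-2). Counting the lost week as 0% is enough to close this gap, since the mid-course stopper then averages (100 + 0)/2 = 50%. The per-week requirement goes slightly further and also prevents an excess in one week from offsetting a shortfall in the other. The descriptive compliance table in SAP 13 can stay as it is.

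The cost is a small change to the set flag, using tablet counts already collected. The completer sets may become slightly smaller; subjects who took all planned tablets in both weeks remain in them.
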